6.6 Exploratory Endpoints

- Novel biomarkers for diagnosis and monitoring of cardiomyopathy in DMD including but not limited to change from baseline in miRNAs, eicosanoids, claudin-5, CD49d, CPK, hs-Trop, NT-proBNP and structural CMR results
- Change from baseline in daily life activity to evaluate motor function and estimate muscle strength measured by an actigraphy sensor worn for one week at baseline, Month 6 and Month 12; Change from baseline and Month 12 in daily activity at Month 24 or Month 36[†] for the open label population.
- Change from baseline in Quantitative Muscle Testing (QMT) to assess muscle strength; Change from baseline and Month 12 in QMT at Month 24 or Month 36[†] for the open label population.

[†] Note: Change from baseline and Month 12 at Month 36 will only be evaluated for patients who completed these endpoint measurements prior to CPI-IFE-007 Protocol Amendment 04a.

[figure not shown]
7 STUDY DESCRIPTION

7.1 Study Design

CPI-IFE-007 is double-blind, placebo-controlled, multicenter, dose-ranging study with an open-label extension to determine the safety, pharmacokinetics and efficacy of two dose ranges of oral ifetroban in subjects with DMD. DMD patients who meet the inclusion criteria and none of the exclusion criteria will receive oral Investigational Medicinal Product (IMP) once daily for 12 months. Subjects will be randomly assigned to one of three treatment groups, low-dose ifetroban, high-dose ifetroban or placebo, and dosed based on weight. Each treatment group will be evaluated by eight subjects with early stage (LVEF > 45%) and eight subjects with advance stage (historical/current LVEF 35% - 45%) DMD for at least six months and a maximum of 12 months. Subjects who complete 12 months of treatment will be eligible to participate in repeatable open-label extension periods of 12 months. An additional comparator group will be utilized from DMD patients evaluated in an FDA-funded natural history study (NHS) over multiple years matched to CPI-IFE-007 subjects by baseline LVEF, age, and background DMD therapy ([Soslow 2023](#)). The CPI-IFE-007 study is designed to mirror the FDA-funded DMD NHS in terms of procedures, imaging protocol, and endpoint assessments to enable valid comparisons between study populations. This design feature will facilitate the planned supplementation of the placebo arm with matched historical controls. All subjects who receive IMP will be assessed for safety. All subjects with at least one efficacy assessment post-baseline will be evaluated for efficacy. Blood and urine will be collected for standard and novel cardiac biomarkers.

The double-blind study will be conducted with two periods: a screening period of up to 12 weeks and a treatment period of up to 12 months. The open label study consisting of high-dose ifetroban treatment will be conducted in repeatable periods of 12 months.

Figure 7-1 Study Design

CBC = complete blood count; CMP = comprehensive metabolic panel; Coags = coagulation factors; ECG=electrocardiogram, Echo= echocardiography; QMT= quantitative muscle testing; PFT= pulmonary function test; QoL = quality of life; LVEF = left ventricle ejection fraction; CMR=cardiac MRI; PE = physical exam with vitals; PK=pharmacokinetics; W= week, M=month

The total duration of the study participation for each subject is up to 52 weeks. There is a repeatable optional open-label extension period where any subject completing 12 months of treatment is eligible to participate. Recruitment is planned to stop when approximately 48 subjects have completed 12 months of treatment. The end of the study is defined as the last subject's last visit/contact.

7.1.1 Pharmacokinetics

Pharmacokinetic parameters, including peak plasma concentration of ifetroban after administration and its acyl glucuronide metabolite, T_{max} , AUC, Clearance and $t_{1/2}$, will be determined from analysis of collected blood drop samples (Section 11.7.5) using an auto-lancet and dry plasma prep cards. Blood samples (two drops of blood) for PK analysis will be collected at specified times on all subjects.

PK samples (two drops of blood) will be collected on all subjects pre-dose and at 30, 60 (± 5) minutes, 4, 8 and 24 hours (all ± 30 minutes) following the first dose of oral IMP and at steady-state at Day 7 pre-dose and 30 (± 5) minutes post-dose. The last two post-dose samples following

the first dose of IMP and the two steady-state dot-blot blood samples can be collected by subject or parent at home.

7.2 Drugs and Dosages

Oral ifetroban is available as the sodium salt of the free acid and is for investigational use only. The drug is supplied as a capsule dosage form (size # 1, white opaque) for oral administration. Ifetroban capsules are formulated as a dry powder blend and filled into hard gelatin capsules. The formulation consists of ifetroban, mannitol, microcrystalline cellulose, crospovidone, magnesium oxide, colloidal silicon dioxide, and magnesium stearate. Capsules are filled into high density polyethylene bottles and sealed with screw-cap closures. Capsules are only available at one strength of the sodium salt, i.e., 52.5 mg corresponding to a free-acid dose of 50 mg.

Matching placebo capsules are formulated as a dry powder blend filled into capsules. The formulation consists of microcrystalline cellulose, crospovidone, colloidal silicon dioxide, and magnesium stearate. Capsules are filled into high density polyethylene bottles and sealed with screw-cap closures.

The bottles of oral ifetroban or placebo will contain the following information on the label:

PLACEBO OR IFETROBAN CAPSULES 50 MG

Quantity: 75 Capsules

Instruction: Take capsules by mouth as directed.

Store at controlled room temperature, 20°C – 25°C (68°F – 77°F)

Caution: New Drug-Limited by Federal law to investigational use

Cumberland Pharmaceuticals Inc.

Additionally, each individual bottle will be labelled with a unique numeric code that identifies the contents to the unblinded sponsor representative. Subjects will be randomized to low-dose ifetroban, high-dose ifetroban or placebo.

Low Dose: < 35 kg: 50 mg, ≥ 35 kg: 100 mg/day

High Dose: < 35 kg: 150 mg, ≥ 35 kg: 300 mg/day

Table 7-1 Ifetroban Dose Levels & Sub-Groups

DMD Sub-Group	Low Dose	High Dose	Placebo
Early Stage (LVEF > 45%)	8 subjects	8 subjects	8 subjects

DMD Sub-Group	Low Dose	High Dose	Placebo
Advance Stage (current/historical LVEF 35-45%)	8 subjects	8 subjects	8 subjects

Should a subject experience an intolerable toxicity attributed to study drug the dose may be reduced by 50-mg decrements (one capsule) at a time at the investigator's discretion. Any subject receiving 50 mg/day who experiences an intolerable toxicity attributed to study drug will be discontinued from the study. A subject may also have their dose held for up to two weeks to allow a severe adverse event to improve or resolve before considering resuming drug. IMP may resume at the starting dose or a reduced dose at the investigator's discretion, once the toxicity has improved or resolved. Any subject with a serious toxicity that does not improve or resolve after a two week hold of IMP will be discontinued from the study.

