8 STUDY VISITS AND PROCEDURES

8.1 Overview – Schedule of Time and Events

This clinical study will consist of a 12-week Screening Period (Week -12 to Week 0) and a 12-month Treatment Period (Month 0 to Month 12). The study visits occur on the planned dates relative to the first dose of IMP as scheduled. The visit schedule should be adhered to within the visit window indicated.

If a subject is prematurely discontinued from treatment, all assessments planned at the End of Treatment visit should be performed. Prior to all screening assessments, after discussion of participation in the study, the written consent form must be signed and dated. Although the screening assessments for this study are grouped under the heading of a single visit in this protocol, it is possible for them to be performed over more than one site visit if necessary, as long as the twelve-week screening period relative to the first dose of IMP is respected. Furthermore, the site may split the on-site study visits during the treatment period (Day 0, Month 6, Month 12 & Month 24, if applicable) into two visits no more than 7 calendar days apart provided that each of the visit days remain within the protocol established window for the on-site study visits. Subjects that fail screening for exclusion criteria, for example concomitant medications, acute illness (upper respiratory tract infection), required drug-specific discontinuation periods or laboratory tests, may be rescreened for study eligibility.

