After six months of treatment, subjects will return to the site for Month 6 Treatment Visit.

- Record all medication use with start date and dose; check for prohibited medications.
- Inquire about AEs/Serious Adverse Events (SAEs) and IMP tolerability.
- Confirm compliance (subject diary & pill counting) & dietary requirement.
- Perform ECG, a physical exam with vital signs (blood pressure, heart rate, respiration rate, body temperature, weight).
- Obtain blood samples for clinical laboratory tests:
 - Complete Blood Count with differential: must include hemoglobin, hematocrit, platelet count, total white blood cell count with five-part differential count, and total red blood cell count.

- Comprehensive Metabolic Panel: must include serum creatinine, blood urea nitrogen, glucose, total protein, albumin, total bilirubin, alanine aminotransferase, aspartate aminotransferase, alkaline phosphatase, electrolytes (sodium, potassium, chloride), calcium, bicarbonate, and creatine phosphokinase.
- Coagulation Factors: prothrombin time reported as the international normalized ratio (INR) value (PT-INR), partial thromboplastin time (PTT or aPTT).
- Collect urine and blood samples for eicosanoid metabolites and other biomarkers.
- Dispense and administer IMP.
- Optional Month 6 CMR (\pm 7 day window). If Month 6 CMR is declined, a mandatory ECHO should be performed.
- Month 6 PFT including PEF, FVC, FEV1, MIP, and MEP
- Month 6 PedsQL, GI module & NMM
- Month 6 QMT & Actigraphy
- Schedule appointment for next visit.

Should the subject report a new or worsening symptom, additional safety phone calls and/or safety visits may be scheduled at the investigator's discretion and safety labs performed. Any new or worsening abnormal lab should be followed and repeated until back to baseline or resolved.

Month 9 At-home Quality-of-Life surveys

- Complete and return Month 9 at-home PedsQL, GI module & NMM.

Month 12 End of Treatment Visit

After six additional months of treatment, subjects will return to the site for Month 12 End of Treatment Visit.

- Record all medication use with start date and dose; check for prohibited medications.
- Inquire about AEs/Serious Adverse Events (SAEs) and IMP tolerability.
- Confirm compliance (subject diary & pill counting) & dietary requirement.

- Perform ECG, a physical exam with vital signs (blood pressure, heart rate, respiration rate, body temperature, weight).
- Obtain blood samples for clinical laboratory tests:

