9 SUBJECT DISCONTINUATION AND STUDY OR SITE TERMINATION

9.1 Subject Discontinuation

Subjects will be encouraged to complete the study; however, they may voluntarily withdraw at any time. The Investigator will provide a report in the CRF describing the reason for discontinuation. If a subject withdraws before completion, every effort should be made to complete the assessments scheduled during the final scheduled assessment.

A subject may be terminated early from the study for the following reasons:

- The subject elects to withdraw consent from all future study activities, including follow-up.
- The subject is “lost to follow-up” (i.e., no further follow-up is possible because attempts to reestablish contact with the participant have failed).
- The subject dies.
- The subject develops a medical condition or is started on new medication(s) prohibited by the study or not previously mentioned in the list of prohibited medications that, in the opinion of the investigator, may pose additional risks from participation in the study, may interfere with the subject’s ability to comply with study requirements or that may impact the quality of the data obtained from the study.

Subjects who are prematurely terminated from the study will be followed to monitor safety for a minimum of 30 days or until resolution of the disqualifying event, whichever is longer, or until the Independent Safety Monitor, the CPI Director of Medical Affairs and the Principal Investigator determine that the follow-up is complete.

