11.2.3 Per Protocol Population

The Per Protocol (PP) Population will consist of all subjects in the ITT population with no major protocol violations, including violation of inclusion or exclusion criteria or insufficient dosing where the latter includes missing more than 2 consecutive weeks of dosing for any reason or missing >20% of prescribed doses between consecutive visits.

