11.7 Methods for Handling Missing Data

All missing data will be queried. Missing data which are not retrievable through queries will not be imputed. The only exception to this is one supportive analysis with missing LVEF at Month 12 imputed by LVEF at Month 6; subjects missing LVEF at both Month 6 and Month 12 will be excluded from this supportive analysis.

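### SAP 3.3 carries the last observation forward for subjects who stop treatment early, while SAP 4.2 and Protocol 11.7 forbid it; Protocol 7.2 also leaves Month 12 cardiac follow-up unsettled for two toxicity groups

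*Protocol*

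**What the plan says.** **Imputation.** Protocol 11.7 states: "Missing data which are not retrievable through queries will not be imputed". Its one exception is a supportive analysis in which a missing Month 12 LVEF takes the Month 6 value. SAP 4.2 repeats this for the primary and key secondary endpoints and closes by ruling out any other imputation for any endpoint. SAP 3.3, in its general text on endpoints, says that subjects who stop study treatment before week 52 have their data imputed by LOCF, with no limit to particular endpoints. SAP 4.4.4 and SAP Section 8 report no change from the protocol's methods.

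**Toxicity.** Under Protocol 7.2 most subjects with toxicity can have the dose reduced or held. Two groups cannot continue: "Any subject receiving 50 mg/day who experiences an intolerable toxicity attributed to study drug will be discontinued from the study", and "Any subject with a serious toxicity that does not improve or resolve after a two week hold of IMP will be discontinued from the study".

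**What is collected afterwards.** Protocol 8.1: "If a subject is prematurely discontinued from treatment, all assessments planned at the End of Treatment visit should be performed". The End of Treatment visit in 8.1.2 is the Month 12 visit, and its CMR has a window of 7 days either side. Protocol 9.1 adds that if a subject withdraws, "every effort should be made to complete the assessments scheduled during the final scheduled assessment". Subjects terminated early "will be followed to monitor safety for a minimum of 30 days or until resolution of the disqualifying event, whichever is longer".

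**Which values count.** SAP 3.7 runs the double-blind efficacy period to the last study visit for a subject who does not enter the open-label period. SAP 14.3.6 restricts the comparison supplemented with natural history data to subjects whose cardiac data are evaluable at Month 12.

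**The concern.** Two separate weaknesses meet on the Month 12 LVEF and strain comparisons. These are secondary, but LVEF drives the sample size (Protocol 11.1).

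The SAP gives two incompatible instructions for anyone who stops treatment early, for any reason. A programmer following 3.3 and one following 4.2 would analyse different values, and the choice could be made after the data are seen.

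For the two groups in 7.2, the protocol does not separate stopping the drug from leaving the study. A Month 12 value lost or mistimed because of an event attributed to the drug is lost for a reason that arises after randomisation and may differ by arm. The 50 mg rule can act unevenly by construction. Doses fall in 50 mg steps, so a low-dose subject under 35 kg starts at 50 mg with no step left, while a high-dose subject of 35 kg or more has five steps from 300 mg down to 50 mg. The documents give no removal rate, so neither the size nor the direction of any bias is known.

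**Working it through.** **1. What the two SAP rules do to the same subject.** Both examples are hypothetical.

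| Subject | SAP 4.2, primary | SAP 4.2, supportive (LVEF only) | SAP 3.3, LOCF |
|---|---|---|---|
| Stops at month 4, CMR at stopping | no Month 12 value | excluded, no Month 6 value | month 4 LVEF and strain carried to Month 12 |
| Stops at month 8, CMR at Month 6 and at stopping | no Month 12 value | Month 6 LVEF; no strain | month 8 LVEF and strain carried to Month 12 |

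The 4.2 columns assume that the scan at stopping is not itself labelled Month 12. No rule settles that. SAP 3.7 places the scan inside the efficacy period. SAP 4.1 limits summary tables to protocol-scheduled visits without saying whether an early End of Treatment visit is one. SAP 14.3.6 does not define evaluable at Month 12.

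**2. Follow-up of the 7.2 groups.** An End of Treatment CMR is due (8.1, 8.1.2). Neither 8.1 nor 9.1 says when it is done for a subject who stops early. After early termination, 9.1 plans safety follow-up only.

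**3. The plan's own figure.** Inputs from Protocol 11.1: 8 per arm within a disease stage, effect 1.6 SD, two-sided 0.05. For the t-test the noncentrality is 1.6 × √(8×8/16) = 3.2 on 14 degrees of freedom, which gives power 84.5% (stated: above 85%). The exact Wilcoxon test, simulated with 100,000 draws, gives 82.2% (stated: above 80%). The figures are reproduced to within rounding.

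**4. Possible bias (assumptions, not trial data).** An arm has 8 + 8 = 16 subjects over both stages. Let k be the extra removals in one arm and d the deficit of those subjects, in SD, against the rest of that arm. If their values are dropped, the mean of the remainder exceeds the full-arm mean by (k/16) × d.

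| k | d | Bias (SD) | Share of 1.6 SD | Type I error | Exact size at that n | Excess (points) |
|---|---|---|---|---|---|---|
| 1 | 0.5 | 0.031 | 2.0% | 5.06% | 4.94% (15 v 16) | 0.12 |
| 1 | 1 | 0.0625 | 3.9% | 5.18% | 4.94% (15 v 16) | 0.24 |
| 2 | 0.5 | 0.0625 | 3.9% | 4.93% | 4.72% (14 v 16) | 0.21 |
| 2 | 1 | 0.125 | 7.8% | 5.86% | 4.72% (14 v 16) | 1.14 |

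Type I error is for the exact two-sided Wilcoxon test at 0.05, with 16 − k against 16 analysed, equal full-arm means and 200,000 simulations per row. The reference must be the exact size at the same sample sizes. The size at 16 v 16 is 4.68%, so comparing with that figure would count discreteness of the test as inflation.

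**5. Scale for k.** The all-cause dropout allowance is 54 − 48 = 6 in SAP 3.4, or 2 per arm, and 60 − 48 = 12 in Protocol 11.1, or 4 per arm. Removals under 7.2 are only part of either figure.

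**The case against.** **The governing imputation rule can be found.** Straight after the LOCF sentence, SAP 3.3 refers the reader to 4.2 for missing data. Section 4.2 is explicit and agrees with the protocol, so the LOCF line reads as stray text. This stands as to which rule should win. It does not remove the conflict, because the LOCF sentence is an unqualified instruction, and SAP 4.1 bars imputation only where nothing else is stated.

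**A Month 12 scan may already be intended.** A reader might infer that no CMR at actual Month 12 is planned for the 7.2 groups. The documents do not support that. The only End of Treatment visit is the Month 12 visit, and 9.1 speaks of the final scheduled assessment. Doing the scan at stopping is the natural reading, but it is an inference. What can be said is that the timing is unstated.

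**Some apparent gaps are choices.** Strain has no carry-forward because the protocol allows a single exception, for LVEF. Protocol 8.1.2 says "If Month 6 CMR is declined, a mandatory ECHO should be performed", but the endpoint is LVEF by CMR, so an ECHO value is not naturally a substitute. Neither point carries weight here.

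**Off-drug values change the question.** The endpoint is efficacy over 12 months of dosing, so including off-drug Month 12 values is a choice of estimand. That is fair, and the plan should make the choice openly. The by-arm summary of missing LVEF and the conditional multiple imputation in SAP 4.2 help to describe or model a gap, but they do not collect the value.

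**Conclusion.** The point holds at low severity. The contradiction between SAP 3.3 and SAP 4.2 with Protocol 11.7 is plain on the text. It affects every subject who stops treatment early, so it would be wrong to tie it to the two toxicity groups alone. The unsettled follow-up of those groups under 7.2 is a separate weakness.

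The likely effect is small. Under the assumed removals the bias is 0.03 to 0.13 SD, or 2% to 8% of the planned effect. Type I error stays near nominal, except for about one point above the exact size of 4.7% at 14 v 16 when two extra subjects are removed from one arm and are 1 SD worse. These figures rest on k and d, for which the documents give no values.

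A reader might infer that the primary endpoint is compromised. It is not: a subject removed under 7.2 has already had a toxicity after dosing, which SAP 7.1 counts as treatment-emergent. Nor is this mainly a loss of power, since Protocol 7.1 plans recruitment until about 48 subjects have completed 12 months.

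**What to change.** 1. Delete the LOCF sentence in SAP 3.3, leaving 4.2 and Protocol 11.7 as the single rule.
2. State in the SAP that an End of Treatment CMR outside the Month 12 window is used only in a supportive analysis, and apply the same rule to Month 12 evaluability in 14.3.6.
3. In both sentences of Protocol 7.2, have the subject discontinued from IMP only. Add that, unless consent is withdrawn, he keeps the scheduled Month 12 CMR. Align 8.1 and 9.1 so that assessments done at stopping do not replace it. Apply this to subjects still in the study; the criteria for stopping drug stay as they are.

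Items 1 and 2 are SAP wording and should be settled before database lock. Item 3 needs a protocol amendment with IRB approval (Protocol 14.2), and possibly revised consent. It adds burden for a few subjects with unresolved toxicity, although the scan is already in the schedule. SAP 4.3 reports the interim analysis as done, so the trial is well advanced and item 3 may reach few subjects.

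Some ITT values would then be off-drug. The per-protocol population excludes subjects "missing more than 2 consecutive weeks of dosing for any reason", so an on-drug view remains. Adverse events recorded after stopping should be flagged as off-drug.

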7.3 Selection of Study Population

Study eligibility will be determined by the Investigator based on the inclusion and exclusion criteria below.

7.3.1 Inclusion Criteria

Individuals who meet all of the following criteria are eligible for enrollment as study subjects:

1. Males 7 years of age and older with the diagnosis of DMD, defined as phenotype consistent with DMD and either positive genotype, first degree relative with positive genotype, or confirmatory muscle biopsy.
2. Stable dose of oral corticosteroids for at least 8 weeks or has not received corticosteroids for at least 30 days.
3. Stable cardiac function defined as change in LVEF of < 15% and no heart failure admission over the last 12 months; LVEF 35% or greater by cine CMR or echocardiography; myocardial damage in one or more left ventricular segments evident by late gadolinium enhancement allowed; concurrent angiotensin-converting enzyme inhibitors (ACEI), beta-blocker (BB) or angiotensin receptor blocker (ARB) therapy allowed (selection of which dictated by clinical care) if started three months or greater from first dose of IMP without change in dose. Aldosterone receptor antagonists (e.g. spironolactone or eplerenone) allowed if started 12 months or greater from first dose of IMP. No changes throughout the study allowed except in the event of a decline in left

ventricular ejection fraction (LVEF) >5% following the baseline CMR as measured by a subsequent CMR at the same center. Should this occur, changes in cardiac medications are allowed on study, and the patient may remain on IMP.

- a. **Late-stage cohort:** Subjects are eligible for the late-stage cohort if the subject has:
 - i. LVEF 35%-45% by cine cardiac magnetic resonance imaging (MRI) or echocardiography or
 - ii. historically documented LVEF 35%-45% by cine cardiac magnetic resonance imaging (MRI) or echocardiography and if their baseline MRI is less than 50%.
4. Subjects aged 18 years and older, informed consent obtained directly. For subjects ages 7–17 years old (yo), both assent from the subject and permission from a parent or guardian.
5. AAV-based gene therapy permitted if ≥ 2 years from AAV administration and subject has documented cardiac decline defined as >5% decline in LVEF over a 2-year period following AAV administration using consecutive CMRs or echocardiography performed at the same center (must still meet inclusion criterion #3).

